	Class II	Diffuse astrocytoma, mixed oligoastrocytomas, oligodendrogloma, pleomorphic xanthoastrocytoma, hairy myxoid astrocytoma
	Class III	Anaplastic astrocytoma, anaplastic oligodendrogloma, anaplastic oligoastrocytomas
	Class IV	Primary and secondary glioblastoma

Isocitrate dehydrogenase (IDH), located in the long arm of chromosome 2 (2q33), is a key rate-limiting enzyme in the tricarboxylic acid cycle, providing energy for cell metabolism and precursors of biosynthesis. There are three isomerases in the IDH gene family (IDH1, IDH2 and IDH3). IDH1 or IDH2 mutations lead to the accumulation of 2-hydroxyglutaric acid, another new metabolite, in cells, which can not only lead to abnormal histone modification, but also increase the activity of VEGF pathway, thereby inducing tumorigenesis. The data showed that IDH1/2 gene mutation was an early genetic mutation in the development of glioma. It usually occurs in young adults and

adolescents with diffuse glioma. IDH1/2 mutation had a certain distribution pattern corresponding to WHO classification, which was mainly distributed in grade II~III oligodendrogloma (69.2%), astrocytoma (79.8%), oligoastrocytomas (75.5%) and grade IV secondary glioblastoma (73%), but rare in primary glioblastoma (<5%) and childhood glioblastoma.

IDH1 mutations accounted for more than 90% of IDH1 and IDH2 gene mutations, among which IDH1 R132H (CGT>CAT, arginine replaced by histidine) mutations were the most common, accounting for about 90% of IDH1 mutations.

The National Comprehensive Cancer Network (NCCN) Clinical Practice Guidelines for Central Nervous System Cancer (V1, 2015) include the presence or absence of IDH1 or IDH2 gene mutations as one of the indicators to assess the risk type of patients with low-class glioma. The Chinese Guidelines for molecular Diagnosis and Treatment of glioma (2014) also included IDH1 or IDH2 gene mutation as the preferred molecular marker for molecular pathological typing (grade I evidence).

At present, the gold standard method for clinical detection of IDH gene mutation is nucleic acid sequencing. However, this method is time-consuming and laborious to determine the detection results, and the operation process is complex, so it is difficult to widely apply this technique in clinical practice.

2 Research Purpose

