3.1 Overall Design of the Trial

This study followed the principle of synchronous blind method. Enrolled cases were coded and compared with the nucleic acid sequence determination of the control method (gold standard). Results were determined independently according to the critical value or interpretation requirements provided by each method, and relevant statistics were conducted. Combined with the results of clinicopathological classification, the incidence of IDH1 gene R132H mutation in different subtypes was counted to evaluate the clinical application performance of this product

The total number of samples for clinical research should be no less than 1,000 cases, and clinical trials should be carried out in no less than 3 (including 3) provincial health care institutions or specialized hospitals to ensure that the results are statistically significant. All samples should have corresponding basic clinical information, including: patient visiting No. / medical record number/specimen number, age, sex, pathological diagnosis result, etc.

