4.3 Evaluate the conformity between the kit and the reference method

- (1) If the results to be tested and the reference results are both positive or negative, it is regarded as in conformity.
- (2) In the event that the result to be tested is positive and the reference result is negative, or the result to be tested is negative and the reference result is positive, it is recorded as non-conformity.
- (3) If the result to be tested fails and the reference method has confirmed results, it shall be recorded as non-conformity. The reasons and results of the non-conformity shall be truthfully recorded, and the comparison results shall be repeatedly confirmed when necessary.
- (4) Complete subsequent statistical analysis based on the above statistical results.

5 Statistical methods

Statistical analysis of clinical study data: Kappa test was used for statistical analysis of the comparison between the kit test results and gene sequencing test results, and then the difference between the results obtained by the two methods was compared. If $\text{Kappa} > 0.6$, it was proved that there was no statistical difference between the two methods in detecting IDH1 gene mutations in glioma samples.

6 Duration of clinical trials and its reasons

The clinical study lasted about 6-8 months from the drafting of the protocol, project approval, ethical review, agreement signing, specimen collection, the beginning of the test to the end of the trial, and the report and seal are completed. If the sample collection is smooth and the number of samples meets the test requirements, the clinical trial time can be shortened; if it is not smooth, the time can be appropriately extended.

7 Inclusion criteria, exclusion criteria and rejection Criteria

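### Kappa > 0.6, the plan's only success rule, cannot prove the kit and sequencing agree: with no false positives it passes miss rates of 21% (80% R132H prevalence) to 51% (20%).

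*Combined protocol and SAP*

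**What the plan says.** Section 5 applies a kappa test to the paired kit and sequencing results and adds "and then the difference between the results obtained by the two methods was compared". It names no test, margin, significance level or limit for that comparison. The only decision rule follows: if kappa exceeds 0.6, "it was proved that there was no statistical difference between the two methods in detecting IDH1 gene mutations in glioma samples". No confidence interval is asked for.

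Other parts of the plan that bear on this:

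- Section 3.1 has the kit "compared with the nucleic acid sequence determination of the control method (gold standard"). Sequencing is therefore the reference, not just a second method.
- Section 3.1 also sets the size: "The total number of samples for clinical research should be no less than 1,000 cases". It gives no derivation and no split by mutation status.
- Section 4.3 sorts each pair into conforming or non-conforming. For kit failures it says: "If the result to be tested fails and the reference method has confirmed results, it shall be recorded as non-conformity". Section 5 does not say how that third outcome enters a two-by-two kappa.
- Sections 3.2.2 and 7.2 allow other brain tumours and normal tissue beside glioma, with no proportions. The R132H prevalence of the study set is thus unknown.

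**The concern.** A kappa above a cut-off shows that agreement is better than chance by some amount. It does not show that two methods give the same answer, and it is not a test of difference. Because it combines both kinds of error in one number, it cannot tell a kit that misses mutations from one that calls them falsely. The miss rate that a fixed cut-off tolerates also changes with prevalence, which the plan leaves open.

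The study's stated purpose is to confirm the kit's performance against sequencing, and this rule is the only criterion for doing so. Followed as written, it could report no difference for a kit that plainly differs from the reference and misses a large share of mutations. The paired data would still allow agreement to be computed. The fault lies in the success criterion and in the conclusion drawn from it.

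**Working it through.** The plan has no power or precision calculation to reproduce: 0.6 and 1,000 are both given without inputs. The check asks which results the rule would accept.

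**Inputs.** From the plan: kappa > 0.6 (Section 5) and n = 1,000 (minimum, Section 3.1). Assumed: R132H prevalence p from 20% to 80%, no kit failures and, at first, no false positives.

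**Formula.** Let m be the share of sequencing-positive samples that the kit misses. With no false positives:

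- observed disagreement = pm
- chance disagreement = p(2 − m − 2p(1 − m))
- kappa = 1 − m / (2 − m − 2p(1 − m))

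Setting kappa = 0.6 gives the limit m = 0.8(1 − p) / (1.4 − 0.8p).

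**Worked example, p = 40%.** The formula gives 0.48/1.08 = 44.4%. In whole samples, take 177 of 400 missed, leaving 223 kit positives. Observed agreement is 0.823. Chance agreement is 0.4 × 0.223 + 0.6 × 0.777 = 0.5554. Kappa = (0.823 − 0.5554)/(1 − 0.5554) = 0.602, a pass. With 178 missed, kappa is 0.599, a fail. All 177 discordant pairs lie in one direction, so exact McNemar p = 2 × 0.5^177 = 1.0e-53.

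**Largest number missed that still passes, n = 1,000, no false positives**

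| Prevalence | Missed | Miss rate | Kappa | Exact McNemar p |
|---|---|---|---|---|
| 20% | 103/200 | 51.5% | 0.601 | 2.0e-31 |
| 40% | 177/400 | 44.2% | 0.602 | 1.0e-53 |
| 50% | 199/500 | 39.8% | 0.602 | 2.5e-60 |
| 60% | 208/600 | 34.7% | 0.601 | 4.9e-63 |
| 80% | 168/800 | 21.0% | 0.601 | 5.3e-51 |

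**Prevalence from the plan's own background figures.** The introduction gives IDH1/2 mutation rates of 69.2% to 79.8% in grade II–III subtypes, says IDH1 makes up more than 90% of these, and describes R132H as "accounting for about 90% of IDH1 mutations". With IDH1 at exactly 90%:

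- 0.692 × 0.9 × 0.9 = 56%; limit 207/560 missed (37.0%)
- 0.798 × 0.9 × 0.9 = 65%; limit 206/650 missed (31.7%)

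If every mutation were IDH1, the top of the range is 0.798 × 0.9 = 72%; limit 195/720 missed (27.1%).

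**Imperfect specificity, p = 40%.** At 98% specificity (12 false positives) the limit is 167/400 missed (41.8%). At 95% (30 false positives) it is 152/400 (38.0%).

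**Would McNemar rescue the rule?** Take p = 40% with 95 false negatives (23.8%) and 95 false positives (15.8%). Observed agreement is 0.81 and chance agreement is 0.4² + 0.6² = 0.52, so kappa = 0.29/0.48 = 0.604. McNemar p = 1 because the errors balance. Such a kit passes both.

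**Would a confidence bound rescue it?** With the large-sample standard error, requiring the lower 95% limit of kappa to exceed 0.6 still passes 158/400 missed (39.5%) with no false positives. It also passes 84 false negatives with 84 false positives (kappa 0.650, lower limit 0.602, McNemar p = 1).

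**The case against.** The strongest reply is that these are tolerance limits, not expected results. A kit with 95% positive and 98% negative agreement would have kappa of about 0.87 to 0.93 over the same prevalence range, far above 0.6. That is true, but a success rule has to be able to fail a poor kit, and this one often would not.

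A second reply is that the clause on comparing the difference may mean a paired test, which would flag every table with one-sided errors. The plan does not name such a test or tie a decision to it, and the balanced example shows that it would not be enough.

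Three narrower points stand in part:

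- **Prevalence.** It is assumed. The plan's own subtype figures put R132H at no more than about 72%, so the 80% row favours the plan.
- **Denominator.** Section 5 concludes about glioma samples only, so the number entering kappa may be below 1,000. The miss-rate limits barely depend on n; the p-values and interval widths do.
- **Kit failures.** Section 4.3(3) and (4) already classify failures as non-conforming and base later analysis on that. Only the way they enter kappa is open.

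The plan also says that results will not guide patients' treatment and no data are lost, so the fault can be repaired before analysis. That does not make the stated inference valid.

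**Conclusion.** The concern holds, with high confidence, and must be fixed before analysis. The invalidity of the inference needs no assumption: exceeding a kappa cut-off does not prove that two methods do not differ, and nothing else in the plan supplies a valid criterion.

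The size does rest on assumptions: 1,000 analysed samples, no kit failures and, for the headline limits, no false positives. The tolerated miss rate then runs from 21% to 51% as prevalence falls from 80% to 20%, and from about 27% to 37% at the 72% to 56% that the plan's grade II–III figures support. False positives use up part of this tolerance but leave it large.

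**What to change.** Replace the Section 5 rule:

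1. Make positive and negative percent agreement against sequencing the primary results, each with a Wilson or exact 95% confidence interval. Declare success only if both lower limits exceed minimum values that the sponsor sets and justifies in advance.
2. Report overall agreement, kappa with its 95% interval, and the paired difference with its interval and exact McNemar test as supporting results. State that neither a kappa cut-off nor a non-significant McNemar test is proof of no difference.
3. Count a failed kit result with a valid sequencing result as a disagreement in the agreement denominators, in line with Section 4.3(3). Show a valid-results-only analysis beside it, and say which set kappa and the paired difference use.
4. Delete the claim of proof. As a minor wording point, limit the conclusion to IDH1 R132H, the only mutation that the kit's result table covers.

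**Cost.** This is a rewording of Section 5 and a little more analysis of data already planned. Precision depends on the mix of samples. With 400 positives, 380/400 gives a Wilson interval of 92.4% to 96.7%, and 588/600 negatives gives 96.5% to 98.9%. With fewer positives the lower limit drops: 91.0% for 190/200 and 83.8% for 47/50. Whether 1,000 samples are enough therefore depends on the number of positives and the minimum values chosen, and the plan should state both.

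The new criterion is stricter than the present one, and counting failures lowers agreement. With an assumed 5% failure rate among 400 positives, 361/380 (95.0%) becomes 361/400 (90.3%).

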By using this product to detect the IDH1 R132H gene mutation in the cancer cells of patients with glioma, compare it with the results of nucleic acid sequence determination, and combine the results of clinicopathological typing to confirm and evaluate the safety and effectiveness of this product.

3 Trial Design

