4.2 Evaluation method for nucleic acid sequence determination

- (1) The results of the positive reference substance tested on the machine for nucleic acid sequence determination were positive, and the results of the blank reference substance should be in line with expectations without mutation detection.
- (2) Determination of reagent results: the sequencing software Mutation Surveyor was used to interpret the results. When 6695 G>GA, corresponding mutation is indicated; otherwise, no mutation is indicated.

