7.1 Inclusion criteria

- (1) Be able to provide samples timely according to the requirements of the protocol.
- (2) The pathological examination conforms to the type of tissue sample listed in Table 1, and the tumor content is not less than 50%.
- (3) The sample should have corresponding basic clinical information, including: the patient's visiting No. / medical record No./specimen No., age, sex, and pathological diagnosis result.

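### Section 5 words its conclusion for IDH1 gene mutations in general, but the trial scores IDH1 R132H only, about 90% of them by the plan's own figure (minor; one-phrase edit)

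*Combined protocol and SAP*

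**What the plan says.** The target is named in several places, and all but one name the same thing.

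- **Section 2 (Research Purpose):** "By using this product to detect the IDH1 R132H gene mutation in the cancer cells of patients with glioma".
- **Section 3.1 (Overall Design):** by clinicopathological subtype, "the incidence of IDH1 gene R132H mutation in different subtypes was counted".
- **Section 4.1, Table 2:** one mutation row, IDH1 R132H, read on the FAM channel.
- **Section 4.2(2), sequencing:** "When 6695 G>GA, corresponding mutation is indicated; otherwise, no mutation is indicated".
- **Section 4.3(1):** "If the results to be tested and the reference results are both positive or negative, it is regarded as in conformity".
- **Section 5 (Statistical methods):** a Kappa above 0.6 is taken to prove "no statistical difference between the two methods in detecting IDH1 gene mutations in glioma samples".

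The background text before Section 2 keeps the two terms apart: "IDH1 R132H (CGT>CAT, arginine replaced by histidine) mutations were the most common, accounting for about 90% of IDH1 mutations".

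**The concern.** Section 5 is the only sentence that says what a passing Kappa establishes, so a clinical report would naturally take its conclusion from there. Its wording covers IDH1 mutations as a class, while both methods are read for one of them.

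The background also says that guidelines use IDH1 or IDH2 mutation status for risk assessment and molecular typing. Someone who meets the Section 5 conclusion on its own could take a kit-negative result as evidence against any IDH1 mutation. The trial is not set up to support that.

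A second, smaller matter lies in 4.2(2). The rule names only the mixed call G>GA and sends everything else to no mutation. The background describes R132H as CGT>CAT, a G-to-A change. Taken literally, a trace showing only A would be reference-negative, and a correct kit positive would become a non-conformity under 4.3(2).

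**Working it through.** The plan gives no calculation to reproduce; the threshold of 0.6 and the 1,000 samples are stated without derivation. The main check is to follow one kind of sample through the rules.

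**Step 1. A sample with an IDH1 mutation other than R132H.**
- Sequencing, 4.2(2): not the named change, so no mutation.
- Kit, Table 2: negative, if the kit is R132H-specific (assumed; the documents give no cross-reactivity data).
- 4.3(1): both negative, so in conformity.

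For R132H this is a true negative. Kappa cannot tell it from a sample with no IDH1 mutation at all.

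**Step 2. Share outside the target.** R132H share about 0.90 (background), so 1 − 0.90 = about 0.10 of IDH1 mutations.

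**Step 3. Kappa as planned.** Kappa = (Po − Pe)/(1 − Pe), where Po is observed and Pe chance agreement. For a kit perfect on R132H there are no discordant pairs, so Po = 1 and Kappa = 1.00, however many other IDH1 variants are in the set.

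**Step 4. Illustration only: the same kit against any IDH1 mutation.** The plan does not run this comparison and gives no prevalence for its sample. Take N = 1,000 (the minimum in 3.1) and an assumed prevalence.

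| Assumed IDH1 prevalence | Both positive | Kit negative, IDH1 mutated | Both negative | Po | Pe | Kappa |
|---|---|---|---|---|---|---|
| 10% | 90 | 10 | 900 | 0.990 | 0.828 | 0.942 |
| 50% | 450 | 50 | 500 | 0.950 | 0.500 | 0.900 |
| 80% | 720 | 80 | 200 | 0.920 | 0.632 | 0.783 |

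For example, at 10%, Pe = (90 × 100 + 910 × 900)/1,000² = 0.828 and Kappa = (0.990 − 0.828)/(1 − 0.828) = 0.942. The 80% row is an outer limit, not an expected value. It applies roughly the highest subtype rate in the background (79.8%, for IDH1 and IDH2 together) to the whole sample, although the background puts primary glioblastoma below 5%, and 3.2.2 and 7.2 also allow other brain tumors and normal tissue. In every row the kit finds 90% of IDH1 mutations and Kappa stays above 0.6.

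**Step 5. The A-only query.** Assume 450 R132H-positive and 550 negative samples, a perfect kit, and 1 to 9 A-only traces scored reference-negative.
- 1 trace: Po = 0.999, Pe = (450 × 449 + 550 × 551)/1,000² = 0.5051, Kappa = 0.998.
- 9 traces: Po = 0.991, Pe = (450 × 441 + 550 × 559)/1,000² = 0.5059, Kappa = 0.982.
- For Kappa to fall to about 0.60 would take some 190 of 450: Po = 0.810, Pe = 0.524, Kappa = 0.286/0.476 = 0.601.

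The documents give no frequency for such traces. With at least 50% tumor content required (7.1), up to half of a sample may be non-tumor tissue, which would normally leave some G signal.

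**The case against.** The strongest reply is that the Section 5 wording is shorthand. The sentence compares two methods, both defined earlier for R132H. Section 3.2.5 ties the sequencing to the sites and types that the kit targets, and Section 2 states the purpose as R132H. Read as a whole, the plan leaves little doubt about the target. This stands as an account of what was meant, and it is a reason to make the edit. It does not correct the stated conclusion, because the background uses the two terms for different things.

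A reader might go further and infer that the trial hides kit failures by counting missed IDH1 mutations as agreement. The documents do not support that. A variant other than R132H is a correct negative for this target. Nor is it established that the kit reads all such variants negative; if it reacted to one, 4.3(2) would record a non-conformity.

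A reader might also infer that 4.2(2) misclassifies true positives. That does not follow either. G>GA may be how the sequencing software writes any R132H call, and the plan does not say outright that 6695 is the R132H base. That link is inferred from the reference to the corresponding mutation, the CGT>CAT description and 3.2.5. This part is a question to the sponsor and not an error shown.

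**Conclusion.** The point holds as one of scope and is minor. Section 5 claims agreement on IDH1 gene mutations, and the evidence will concern IDH1 R132H. The gap is about 10% of IDH1 mutations by the plan's own approximate figure. It affects what the trial may conclude; the planned scoring and Kappa are sound for the R132H purpose.

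The conclusion rests on two assumptions: that the change named in 4.2(2) is R132H, and that the kit is R132H-specific. The scope mismatch between Section 5 and Sections 2, 3.1 and Table 2 needs neither of them. The Kappas against any IDH1 mutation are illustrations at assumed prevalences and are not predictions for this trial.

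The A-only matter is unresolved by the documents. At the small counts tried its effect on Kappa is under 0.02 and runs against the kit, so a change in pass or fail is unlikely.

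**What to change.** 1. In Section 5, replace the reference to IDH1 gene mutations with *the IDH1 R132H mutation*.
2. In 4.2(2), confirm whether G>GA also covers a trace showing only A at 6695, and say so if it does. If it does not, confirm that 6695 is the R132H base and then count such a trace as R132H-positive.

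The first edit changes no count, Kappa or sample size; its only downside is a narrower claim. The second is a clarification that needs no new samples or tests. It would alter a result only if A-only traces occur and are now scored negative.

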7.1 Inclusion criteria

- (1) Be able to provide samples timely according to the requirements of the protocol.
- (2) The pathological examination conforms to the type of tissue sample listed in Table 1, and the tumor content is not less than 50%.
- (3) The sample should have corresponding basic clinical information, including: the patient's visiting No. / medical record No./specimen No., age, sex, and pathological diagnosis result.

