3.2.2 Sample data

- (1) Sample information
 - A) Patient visiting No. / medical record No. / specimen No., age, sex, and pathological diagnosis result
 - B) HE staining results of samples, indicating tumor area.
- (2) Pathological examination confirmed glioma, other brain tumors or normal tissues.
- (3) Number of samples: each sample contains 10 slices with a thickness of 10 μ m, and the tumor content is not less than 50%.

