3.3 Study technology route

3.4 Quality control method

- (1) The clinical verification institutions are all three-level medical institutions above the provincial level with the ability to conduct the clinical research technology and equipment to ensure the quality of clinical diagnosis.
- (2) Each clinical trial institution has 1 project director, and 1 to 3 fixed project members. Strictly follow the requirements of the clinical trial protocol. The reporting institution appoints 1 inspector to monitor and cooperate with the team leader institution and the trail institution at any time. The technical personnel of the team leader institution keep close contact with each trail center at any time.
- (3) The test kit detection and reference method detection are carried out in accordance with the blind method.
- (4) Hospital laboratories participating in clinical trials should establish standard operating procedures and quality control procedures for experimental observation indicators. The test report must be complete, which must include date, test items, test results and their normal range. The person concerned should sign. Each test is set up control, and strictly in accordance with the requirements of the manual.
- (5) Training: Before the start of the experiment, conduct protocol training for all personnel participating in the experiment, and conduct training and assessment for clinical research staff, so that clinical trial personnel able to quickly become familiar with and master the fluorescence PCR technology and the applicable instruments, operating methods, and technical performance etc. of the kit.
- (6) This protocol has been determined through repeated communication and research between the experimental institution and the clinical institution, and must be strictly implemented. Any changes in the plan must be approved by the team leader (master) institution.

4 Evaluation method

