7.2 Exclusion criteria

Those who do not meet any of the above conditions are excluded.

Rationale: Included glioma, other brain tumors, and normal samples should be statistically significant and the conclusions obtained are scientifically valid. The selection of subjects for this study, while excluding research-related influencing factors, has no adverse effect on the health of the subjects.

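### Kappa is not restricted by tissue type although its conclusion is for glioma samples only, and the 50% tumour rule conflicts with the listed normal tissue

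*Combined protocol and SAP*

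**What the plan says.** **Which samples are in the study.** Section 3.2.2(2) describes the samples as "Pathological examination confirmed glioma, other brain tumors or normal tissues". The rationale in section 7.2 takes the same view: "Included glioma, other brain tumors, and normal samples should be statistically significant and the conclusions obtained are scientifically valid".

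**Which samples are eligible.** Inclusion criterion 7.1(2) reads "The pathological examination conforms to the type of tissue sample listed in Table 1, and the tumor content is not less than 50"%. Section 3.2.2(3) sets the same floor for every sample: it opens "Number of samples: each sample contains 10 slices with a thickness of 10" μm and ends "and the tumor content is not less than 50"%. Neither item exempts normal tissue.

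**Which samples enter the analysis.** Section 4.3 classes each pair of results as conforming or not, without separating tissue types, and item (4) bases the later statistics on that classification. Section 5 applies kappa to the kit and sequencing results and names no analysis set. If kappa exceeds 0.6, it concludes that "there was no statistical difference between the two methods in detecting IDH1 gene mutations in glioma samples". The purpose in section 2 is also about glioma: "By using this product to detect the IDH1 R132H gene mutation in the cancer cells of patients with glioma".

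**Size.** Section 3.1 asks for no fewer than 1,000 cases, without a split between glioma, other brain tumours and normal tissue.

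**The concern.** The data going into kappa and the population the conclusion is about are not the same on paper. Kappa is the only statistic in the plan with a threshold. Normal tissue, and possibly other brain tumours, would be expected to be mostly negative by both methods. If such samples are pooled with the gliomas, agreement looks better although nothing has changed in the tissue the conclusion concerns.

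The eligibility text does not settle the matter. Read literally, 7.1(2) keeps normal tissue out. Read with 3.2.2(2) and the 7.2 rationale, normal tissue is in. Two competent statisticians could therefore build different kappa tables from the same data, and each could cite the protocol.

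**Working it through.** **Step 1: eligibility.** Normal tissue contains no tumour. Since 0% is below 50%, it fails 7.1(2) and 3.2.2(3), while 3.2.2(2) and the 7.2 rationale count it as included. This needs only the 50% rule. Other brain tumours can meet the 50% rule, but 7.1(2) also requires a Table 1 tissue type. The rows of Table 1 that can be read (Classes II to IV) list only gliomas. The start of the table is not available, so this second conflict is possible but not established.

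**Step 2: direction of the effect on kappa.** Let a = both methods positive, b and c = the two kinds of discordant result, d = both negative. Then

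kappa = 2(ad − bc)/(dS + T), with S = 2a + b + c and T = b(a + b) + c(a + c).

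The derivative with respect to d has the sign of 2a(dS + T) − 2(ad − bc)S = 2aT + 2bcS. This is positive whenever a > 0 and b + c > 0. Adding concordant negatives therefore raises kappa whenever there is at least one concordant positive and one discordant result. Kappa does not depend on scale, so this also holds when the total is fixed at 1,000.

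**Step 3: size, under assumptions.** From the plan: a total of 1,000 (section 3.1, a minimum) and the 0.6 threshold (section 5). Assumed, because the plan gives no values: G gliomas and N non-glioma samples, all concordant negative, with G + N = 1,000; share p of gliomas mutated; positive agreement = negative agreement = s. The expected table is a = Gps, b = G(1 − p)(1 − s), c = Gp(1 − s), d = G(1 − p)s + N, and kappa = (po − pe)/(1 − pe).

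Example with p = 0.7 and s = 0.85:
- N = 0: a = 595, b = 45, c = 105, d = 255; po = 0.850, pe = 0.556; kappa = 0.294/0.444 = 0.662.
- N = 300, G = 700: a = 416.5, b = 31.5, c = 73.5, d = 478.5; po = 0.895, pe = 0.501; kappa = 0.790.

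All cases at s = 0.85:

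| N of 1,000 | p = 0.3 | p = 0.5 | p = 0.7 |
|---|---|---|---|
| 0 (glioma only) | 0.662 | 0.700 | 0.662 |
| 50 | 0.670 | 0.714 | 0.693 |
| 100 | 0.678 | 0.727 | 0.719 |
| 200 | 0.692 | 0.750 | 0.759 |
| 300 | 0.705 | 0.769 | 0.790 |

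The rise is 0.008-0.031 with N = 50 and 0.043-0.127 with N = 300. At s = 0.95 the largest rise over the same grid is 0.883 to 0.930 (p = 0.7, N = 300), about 0.05.

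**Step 4: precision of a glioma-only kappa.** This uses 1.96 × the large-sample standard error of kappa (Fleiss-Cohen-Everitt) at s = 0.85 and p = 0.3 to 0.7. The half-width is 0.044-0.049 with 1,000 gliomas, 0.045-0.050 with 950 and 0.053-0.059 with 700. The ratio is √(1000/G): √(1000/950) = 1.03 and √(1000/700) = 1.20.

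The plan's figure of 1,000 cannot be reproduced, since no expected kappa, precision, alpha or power is given. Nothing above depends on its derivation.

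**The case against.** A tumour-content floor is naturally read as applying to samples that contain tumour, so the eligibility conflict is largely one of wording. The operative criterion, 7.1(2), taken literally excludes normal tissue, and then no normal sample reaches kappa. Both the purpose and the section 5 conclusion refer to glioma, which points toward a glioma-only analysis. Section 3.4(5) requires the sponsor to "conduct protocol training for all personnel participating in the experiment", and 3.4(2) keeps the lead institution in contact with the sites, so divergent reading by sites is less likely.

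Most of this stands, and it limits the weight of the point. It does not remove it. Training and oversight do not define an analysis set. The rejection criteria in 7.3 do not mention tissue type. The glioma wording in section 5 describes the conclusion, not the data going in, and 4.3 pools without distinction.

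A reader might infer that pooling would turn a failed trial into a passed one. That can be constructed: at an assumed 80% agreement with 70% of gliomas mutated, 10% concordant negatives move kappa from 0.558 to 0.629. But the 80% was chosen to lie near the threshold. The documents give neither an expected agreement nor a number of non-glioma samples, so they do not support that claim.

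**Conclusion.** The point holds as a gap to be closed before analysis. The set of samples entering kappa is not defined and, as written, may be wider than the population in the conclusion. Pooling concordant-negative non-glioma samples moves kappa upward; that direction is certain under the mild condition in step 2. The size is not derivable from the documents. It is 0.01-0.13 at an assumed 85% agreement and at most about 0.05 at 95%, where kappa is well above 0.6 with or without pooling. No change of pass or fail is claimed.

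The eligibility contradiction for normal tissue is certain on the visible text, although the likely intent is plain. It would go too far to say that other brain tumours are ineligible, because Table 1 is only partly visible; they may fail 7.1(2). Nor do the documents show that non-glioma samples will in fact be pooled. They only leave it open.

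**What to change.** 1. In section 5, state that the kappa compared with 0.6 is computed on glioma samples only, whichever eligibility wording is chosen. Tabulate kit and sequencing results for other brain tumours and for normal tissue separately.
2. Reconcile 3.2.2(2)-(3), 7.1(2) and the 7.2 rationale. Either limit the 50% rule to tumour samples and name the non-glioma sample types as eligible, or delete the sample types that are not eligible.
3. In section 3.1, state whether non-glioma samples count toward the minimum of 1,000.

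The cost is a few sentences. No new data are needed, because the pathological diagnosis already required for every sample identifies the tissue type. The downside arises only if non-glioma samples count and the total stays at exactly 1,000: the glioma-only kappa interval is then about 3% wider with 950 gliomas and 20% wider with 700. Since 1,000 is a minimum, this can be avoided by collecting beyond it, at the price of the extra samples.
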